**Contacts for SAE reporting are specified in [Appendix 3](#).**

#### **9.2.1      *Time Period and Frequency for Collecting AE and SAE Information***

Section 5.6 in the IB represents the Reference Safety Information to determine expectedness of SAEs for expedited reporting.

All AEs and SAEs must be collected from the time of signing the consent, including those thought to be associated with protocol-specified procedures for a minimum of 100 days after the last dose, except in cases where a study participant has started a new antineoplastic therapy. However, any SAE occurring after the start of a new treatment that is suspected to be related to study treatment by the investigator will be reported. For participants assigned to treatment and never treated with study drug, SAEs should be collected for 30 days from the date of first dose.

The investigator must report any SAE that occurs after these time periods and that is believed to be related to study drug or protocol-specified procedure (eg, a follow-up skin biopsy).

- Medical occurrences that begin before the start of study treatment but after obtaining informed consent will be recorded on the appropriate section of the eCRF module.
- All SAEs will be recorded and reported to the Sponsor or designee within 24 hours, as indicated in [Appendix 3](#).
- The investigator will submit any updated SAE data to the Sponsor or designee within 24 hours of the updated information being available.

Investigators are not obligated to actively seek AEs or SAEs in former study participants. However, if the investigator learns of any SAE, including a death, at any time after a participant has been discharged from the study and he/she considers the event reasonably related to the study treatment or study participation, the investigator must promptly notify the Sponsor.

The method of evaluating and assessing the causality of AEs and SAEs and the procedures for completing and reporting/transmitting SAE reports are provided in [Appendix 3](#).

#### **9.2.2      *Method of Detecting AEs and SAEs***

AEs can be spontaneously reported or elicited during open-ended questioning, examination, or evaluation of a participant. Care should be taken not to introduce bias when collecting AEs and/or SAEs. Inquiry about specific AEs should be guided by clinical judgement in the context of known AEs, when appropriate for the program or protocol.

All nonserious AEs and SAEs (not only those deemed to be treatment related) should be collected continuously during the treatment period and for a minimum of 100 days following discontinuation after the last dose.

Every AE must be assessed by the investigator with regard to whether it is considered an IMAE. For events that are potentially immune mediated, additional information will be collected on the participant's CRF.

### **9.2.3     *Follow-up of AEs and SAEs***

- Nonserious AEs should be followed to resolution or stabilization or reported as SAEs if they become serious (see [Appendix 3](#)).
- Follow-up is also required for nonserious AEs that cause interruption or discontinuation of study treatment and for those present at the end of study treatment, as appropriate.
- All identified nonserious AEs must be recorded and described on the nonserious AE page of the CRF (paper or electronic). Completion of supplemental CRFs may be requested for AEs and/or laboratory abnormalities that are reported/identified during the course of the study.

All SAEs will be followed until resolution, until the condition stabilizes, until the event is otherwise explained, or until the participant is lost to follow-up (as defined in [Section 8.3](#)).

Further information on follow-up procedures is given in [Appendix 3](#).

### **9.2.4     *Regulatory Reporting Requirements for SAEs***

- Prompt notification by the investigator to the Sponsor of SAEs is essential so that legal obligations and ethical responsibilities toward the safety of participants and the safety of a product under clinical investigation are met.
- An investigator who receives an investigator safety report describing SAEs or other specific safety information (eg, summary or listing of SAEs) from the Sponsor will file it along with the IB and will notify the IRB/IEC, if appropriate according to local requirements.

The Sponsor or designee will report AEs to regulatory authorities and ethics committees according to local applicable laws including European Directive 2001/20/EC and FDA Code of Federal Regulations 21 CFR Parts 312 and 320. A SUSAR (Suspected, Unexpected Serious Adverse Reaction) is a subset of SAEs and will be reported to the appropriate regulatory authorities and investigators following local and global guidelines and requirements.

### **9.2.5     *Pregnancy***

If, following initiation of the study treatment, it is subsequently discovered that a participant is pregnant or may have been pregnant at the time of study exposure, including during at least 5 half-lives after product administration, the investigator must immediately notify the BMS medical monitor/designee of this event and complete and forward a Pregnancy Surveillance Form to the BMS designee within 24 hours of awareness of the event and in accordance with the SAE reporting procedures described in [Appendix 3](#).

If the investigator determines a possible favorable benefit/risk ratio that warrants continuation of study treatment, or re-initiation of study treatment, a discussion between the investigator and the BMS medical monitor/designee must occur. If, for whatever reason, the pregnancy has ended, confirmed by negative serum pregnancy test, treatment may be resumed (at least 3 weeks and not greater than 6 weeks after the pregnancy has ended), following approvals of the participant/Sponsor/IRB/EC, as applicable.

Protocol-required procedures for study discontinuation and follow-up must be performed on the participant.

Follow-up information regarding the course of the pregnancy, including perinatal and neonatal outcome and, where applicable, offspring information, must be reported on the Pregnancy Surveillance Form.

Any pregnancy that occurs in a female partner of a male study participant should be reported to the Sponsor or designee. In order for the Sponsor or designee to collect any pregnancy surveillance information from the female partner, the female partner must sign an ICF for disclosure of this information. Information on this pregnancy will be collected on the Pregnancy Surveillance Form.

In cases where a study drug can be present in seminal fluid, at exposures sufficient to potentially cause fetal toxicity, and if any sexual activity (eg, vaginal, anal, oral) has occurred between a male participant and a pregnant WOCPB partner, the information should be reported to the Sponsor or designee, even if the male participant has undergone a successful vasectomy. In order for the Sponsor or designee to collect any pregnancy surveillance information from the female partner, the female partner must sign an ICF for disclosure of this information. Information on the pregnancy will be collected on the Pregnancy Surveillance Form.

### **9.2.6      *Laboratory Test Result Abnormalities***

The following laboratory test result abnormalities should be captured on the nonserious AE CRF page or SAE Report Form (electronic), as appropriate. Paper forms are only intended as a back-up option when the electronic system is not functioning.

- Any laboratory test result that is clinically significant or meets the definition of an SAE
- Any laboratory test result abnormality that requires the participant to have the study treatment discontinued or interrupted
- Any laboratory test result abnormality that requires the participant to receive specific corrective therapy

It is expected that wherever possible, the clinical rather than the laboratory term would be used by the reporting investigator (eg, anemia versus low hemoglobin value).

### **9.2.7      *Potential Drug-induced Liver Injury***

Wherever possible, timely confirmation of initial liver-related laboratory abnormalities should occur prior to the reporting of a potential drug-induced liver injury (DILI) event. All occurrences of potential DILIs meeting the defined criteria must be reported as SAEs (see [Section 9.2](#) and [Appendix 3](#) for reporting details).

Potential DILI is defined as follows:

- 1) AT (ALT or AST) elevation  $> 3 \times$  ULN  
AND
- 2) TBili  $> 2 \times$  ULN, without initial findings of cholestasis (elevated serum alkaline phosphatase)  
AND
- 3) No other immediately apparent possible causes of AT elevation and hyperbilirubinemia, including, but not limited to, viral hepatitis, pre-existing chronic or acute liver disease, or the administration of other drug(s) known to be hepatotoxic.

### **9.2.8      *Other Safety Considerations***

Any significant worsening noted during interim or final physical examinations, electrocardiogram (ECG), x-ray filming, any other potential safety assessment required or not required by the protocol should also be recorded as a nonserious or serious AE, as appropriate, and reported accordingly.

### **9.3            *Overdose***

For this study, any accidental or intentional administration of any dose of a product that is considered both excessive and medically important will be considered an overdose. All occurrences of overdose must be reported as SAEs (see [Section 9.2](#)).

In the event of an overdose the investigator should:

- 1) Contact the Medical Monitor immediately
- 2) Closely monitor the participant for AEs/SAEs and laboratory abnormalities.
- 3) Document the quantity of the excess dose as well as the duration of the overdosing in the CRF.

Decisions regarding dose interruptions or modifications will be made by the investigator in consultation with the Medical Monitor, based on the clinical evaluation of the participant.

### **9.4            *Safety***

Planned time points for all safety assessments are listed in the Schedule of Activities ([Section 2](#)).

#### **9.4.1        *Physical Examinations***

Refer to the Schedule of Activities ([Section 2](#)).

#### **9.4.2        *Vital Signs***

Refer to the Schedule of Activities ([Section 2](#)).

#### **9.4.3        *Electrocardiograms***

Details regarding electrocardiograms are described in the Schedule of Activities ([Section 2](#)).

#### **9.4.4 Clinical Safety Laboratory Assessments**

- Investigators must document their review of each laboratory safety report.
- Local laboratories will be used for the safety evaluations.
- A local laboratory will perform the analyses and will provide reference ranges for these tests. The clinical laboratory assessments are indicated in Table 9.4.4-1.
- Results of clinical laboratory tests performed on Day -1 must be available prior to dosing.
- Results of all laboratory tests required by this protocol must be provided to BMS, recorded either on the laboratory pages of the CRF or by another mechanism, as agreed upon between the investigator and BMS (eg, provided electronically). If the units of a test result differ from those printed on the CRF, the recorded laboratory values must specify the correct units. Any abnormal laboratory test result considered clinically significant by the investigator must be recorded on the appropriate AE page of the CRF (see [Section 9.2.6](#)).

**Table 9.4.4-1: Clinical Safety Laboratory Assessments**

Hematology - Complete Blood Count		

• Hemoglobin

• Hematocrit

• Total leukocyte count, including differential

• Platelet count

		
Urinalysis (screening only)		

• Creatinine

• Protein

		
Chemistry		

• Aspartate aminotransferase (AST)

• Alanine aminotransferase (ALT)

• Total bilirubin (TBili)

• Alkaline phosphatase (ALP)

• Lactate dehydrogenase (LDH)

• Creatinine

• Blood urea nitrogen (BUN) or serum urea

• Glucose

	

• Albumin (screening only)

• Sodium

• Potassium

• Chloride

• Calcium

• Corrected calcium (screening only)

• Phosphorus

• Magnesium

	

	

• Aspartate aminotransferase (AST)

• Alanine aminotransferase (ALT)

• Total bilirubin (TBili)

• Alkaline phosphatase (ALP)

• Lactate dehydrogenase (LDH)

• Creatinine

• Blood urea nitrogen (BUN) or serum urea

• Glucose

	

• Albumin (screening only)

• Sodium

• Potassium

• Chloride

• Calcium

• Corrected calcium (screening only)

• Phosphorus

• Magnesium

• Aspartate aminotransferase (AST)

• Alanine aminotransferase (ALT)

• Total bilirubin (TBili)

• Alkaline phosphatase (ALP)

• Lactate dehydrogenase (LDH)

• Creatinine

• Blood urea nitrogen (BUN) or serum urea

• Glucose

	

• Albumin (screening only)

• Sodium

• Potassium

• Chloride

• Calcium

• Corrected calcium (screening only)

• Phosphorus

• Magnesium

	
Serology		

• Hepatitis B/C (screening only) (HBVsAg, HCV antibody or HCV RNA)

• HIV, if mandated locally (see Appendix 8)

		
Other Analyses		


• Thyroid stimulating hormone (TSH) with free thyroxine (fT3) and free triiodothyronine (fT4) (screening only)

• TSH with reflexive fT3 and fT4

• Pregnancy test (WOCBP only: minimum sensitivity 25 IU/L or equivalent units of HCG).

• Follicle stimulating hormone (FSH) screening - only required to confirm menopause in women < age 55

		

#### **9.4.5 *Imaging Safety Assessment***

Any incidental findings of potential clinical relevance that are not directly associated with the objectives of the protocol should be evaluated and handled by the study investigator per standard medical/clinical judgment.

#### **9.5 *Pharmacokinetics***

Not applicable.

[figure not shown]
#### **9.6 *Pharmacodynamics***

[figure not shown]
Pharmacodynamic parameters are not evaluated in this study.

[figure not shown]
#### **9.7 *Pharmacogenomics***

[figure not shown]
Not applicable.

[figure not shown]

## **10 STATISTICAL CONSIDERATIONS**

### **10.1 Sample Size Determination**

The sample size of the study is based on a Simon 2-stage design that will test whether retreatment with ipilimumab in combination with nivolumab in patients with mRCC progressing on maintenance nivolumab after first-line therapy with ipilimumab and nivolumab yields a DCR that is of clinical interest.

In this study, a DCR in excess of 20% will be considered of clinical interest. The Simon design will test the null hypothesis that the true DCR is less than or equal to 20% versus the alternative hypothesis that it exceeds 20%. The type I error rate will be 5% for a 1-sided test and the design will have 85% power to reject the null hypothesis when the true DCR is 35%.

The Simon design in this study requires 27 response-evaluable patients for the first stage. The patients included in the first stage analysis will be followed for at least 2 scans approximately 4 months after first dose. The enrollment will not be stopped during the first stage analysis so this relatively shorter follow-up period will be used in order to mitigate risk to patients being enrolled but not included in the first stage analysis. This analysis will quantify patients without progression. For example, confirmed responders, patients with unconfirmed response without progression, and patients with SD on consecutive scans would all qualify as having disease control. If there are exactly 27 patients in the first stage, then 7 or more of these patients, or at least 26%, will warrant proceeding to the second stage. Otherwise, enrollment will be stopped.

The enrollment will stop when either futility is declared at Stage 1 or once approximately 80 response-evaluable participants have been treated. Approximately 96 participants will be enrolled in order to obtain 80 response-evaluable patients, accounting for approximately 20% of

non-evaluable patients or withdrawal. The number of enrolled participants with SD  $\geq$  6 months will be capped at 50%.

The duration of the trial is expected to be approximately 24 months of treatment (Stage 1 + Stage 2) and 36 months of follow-up after the last participant first dosing. A futility analysis will be performed after Stage 1 and the primary analysis will be conducted upon completion of Stage 2.

## 10.2 Populations for Analyses

For purposes of analysis, the following populations are defined:

Population	Description
Enrolled	All participants who sign informed consent and were registered into the IRT
Response Evaluable	All participants with baseline and at least 1 on-study tumor assessment who received at least 1 dose of study treatment. Analysis of demography, protocol deviations, baseline characteristics, and efficacy will be performed on this population.
Safety	All participants who take at least 1 dose of study treatment. This is the primary dataset for drug exposure and safety analysis.

Abbreviation: IRT = interactive response technology.

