## 5 STUDY DESIGN

### 5.1 Overall Design

[figure not shown]
This is a Phase 2, international, multicenter study of rechallenge with ipilimumab 1 mg/kg Q3W combined with nivolumab 3 mg/kg for up to 4 doses followed by nivolumab 480 mg every 4 weeks (Q4W).

- The study will enroll participants previously treated with combination regimen ipilimumab and nivolumab for advanced RCC and mRCC, who had an initial response of CR, PR, or SD for at least 6 months, and who had a confirmed progression on nivolumab maintenance. The number of enrolled participants with SD  $\geq$  6 months will be capped at 50%. Evaluable tumor tissue, recently acquired after confirmed progression, must be obtained prior to treatment initiation.
- Participants should not have experienced any prior AE that meets the criteria for treatment discontinuation as described in [Section 7.4.4](#), with the exception of patients with prior history of adrenal insufficiency that are under control with hormone replacement.
- The study treatment will continue until participants experience disease progression per RECIST 1.1, unacceptable toxicity, or a maximum of 24 months of study treatment with nivolumab. There is a maximum of 4 doses of ipilimumab.

[figure not shown]
- For drug-related toxicities, dosing of both drugs can be delayed and resumed after resolution per protocol-specified criteria (Sections 7.4.2 and 7.4.3, respectively). No dose increases or reductions are allowed for either drug. Management algorithms of the drug-related toxicities, including the use of corticosteroids and other immunomodulating agents, are provided in Appendix 5.
- During the combination phase (Cycles 1 through 4), participants unable to resume nivolumab and ipilimumab for drug-related toxicities will be permitted to proceed to nivolumab monotherapy maintenance (Section 7.4.4).
- Participants should have baseline computed tomography (CT)/MRI scan results showing measurable disease lesion(s) per RECIST 1.1 and first postbaseline tumor assessment at Week 12 followed by subsequent tumor assessments every 8 weeks in the first 60 weeks, and every 12 weeks thereafter (Section 9.1.1 for more details). The tumor assessment schedule should continue until initiation of another anti-cancer treatment. Images will be submitted to a central imaging vendor and may undergo blinded independent central review (BICR) at any time during the study.

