### 10.3.1 Efficacy Analyses

Endpoint	Statistical Analysis Methods
Primary	DCR is defined as the proportion of participants who achieve a confirmed best response of CR, PR, or SD for at least 6 months after first treatment dose using the RECIST 1.1. The number and percentage of participants in each category of BOR (CR, PR, SD, PD, or UTD) as per RECIST 1.1 criteria will be presented. An estimate of the response rate and an associated exact 2-sided 95% CI (Clopper and Pearson) will be presented.
Secondary	OS is defined as the time from first dose date to the date of death from any cause. For participants that are alive, their survival time will be censored at the date of last contact ("last known alive date"). OS will be censored for participants at the date of first dose if they were treated but had no follow-up. A similar analysis as in PFS will be conducted for OS.
	ORR is defined as the proportion of participants who achieve a best response of CR or PR using the RECIST1.1 criteria.
	DOR is defined as the time between the date of first documented confirmed response (CR or PR) to the date of the first documented progression as per RECIST 1.1 or death due to any cause, whichever occurs first. For participants who neither progress nor die, the DOR will be

Endpoint	Statistical Analysis Methods
	
censored at the same time they will be censored for the primary definition of PFS. DOR will be evaluated for responders (ie, participants with confirmed CR or PR) only.

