	
The primary definition of PFS is specified as the time between the date of first dose and the first date of documented progression as per RECIST 1.1 criteria or death due to any cause, whichever occurs first. Participants who die without a reported progression will be considered to have progressed on the date of their death. The following censoring rules will be applied for the primary definition of PFS.
 

• Participants who did not progress or die will be censored on the date of their last evaluable tumor assessment.

• Participants who did not have any on-study tumor assessments and did not die will be censored on their date of first dose.

• Participants who receive subsequent systemic anticancer therapy prior to documented progression will be censored at the date of the last tumor assessment prior to the initiation of the new therapy.

 
Median PFS will be estimated via the Kaplan-Meier product limit method. Two-sided 95% CI for the median PFS will be computed. Kaplan-Meier plots of PFS will be presented. The totality of PFS results will be presented in a single graphical display that includes the Kaplan-Meier curve and the median estimate and corresponding CIs.
 
The secondary definition of PFS is defined as the time between the date of first dose and the first date of documented progression as per RECIST 1.1 criteria or death due to any cause, whichever occurs first. Participants who die without a reported progression will be considered to have progressed on the date of their death. The following censoring rules will be applied for the secondary definition of PFS.
 

• Participants who did not progress or die will be censored on the date of their last evaluable tumor assessment.

• Participants who did not have any on-study tumor assessments and did not die will be censored on their date of first dose.

 
PFS based on investigator assessments will also be analyzed applying both the primary and the secondary definitions.
 
More detail on PFS will be provided in a separate Statistical Analysis Plan.

	
TTR is defined as the time from first dose date to the date of the first confirmed documented response (CR or PR) per RECIST 1.1 criteria. TTR will be evaluated for responders among the population of interest (ie, participants with a BOR of CR or PR).

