### **10.3.5 Interim Analyses**

A futility analysis will be performed after Stage 1 based on a Simon 2-stage design.

- In Stage 1, 27 response-evaluable patients will be enrolled and a futility analysis will be performed.
- In Stage 2 (if Stage 1 positive), 53 response-evaluable more patients will be enrolled.

If there are exactly 27 patients in the first stage, then 7 or more of these patients, or at least 26%, will warrant proceeding to the second stage. Otherwise, enrollment will be stopped.

The Statistical Analysis Plan will further describe the planned interim analyses.

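### Section 10.2 restricts OS and PFS, as well as DCR and ORR, to participants with an on-study scan, while the OS and PFS rules in Section 10.3.1 are written for everyone treated

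*Combined protocol and SAP*

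**What the plan says.** Section 10.2 describes the Response Evaluable population as "All participants with baseline and at least 1 on-study tumor assessment who received at least 1 dose of study treatment" and gives it this role: "Analysis of demography, protocol deviations, baseline characteristics, and efficacy will be performed on this population". No efficacy endpoint is exempted. The Safety population, which needs only one dose, is assigned to exposure and safety. Section 10.3.1 covers DCR, OS, ORR, DOR, PFS and TTR and names no other population for any of them.

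Within Section 10.3.1, both PFS definitions start at first dose, treat a death without reported progression as an event on the date of death, and add: "Participants who did not have any on-study tumor assessments and did not die will be censored on their date of first dose". OS also starts at first dose. It censors living participants at the last known alive date and adds: "OS will be censored for participants at the date of first dose if they were treated but had no follow-up". Table 4-1 states the objective for the additional efficacy measures (ORR, DOR, PFS and TTR) as covering all participants.

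On timing, Section 5.1 sets the "first postbaseline tumor assessment at Week 12". Section 9.1.1 allows extra scans when clinically indicated, and Section 9.1.1.2 continues scans after dosing stops.

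The design counts response-evaluable patients throughout. Section 10.3.5 says "In Stage 1, 27 response-evaluable patients will be enrolled and a futility analysis will be performed", and Section 10.1 closes enrollment at the latest "once approximately 80 response-evaluable participants have been treated". Section 10.3 leaves the selection of participants to a SAP to be finalized before database lock, and Section 10.3.1 leaves further PFS detail to it.

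**The concern.** Membership of the efficacy set depends on something that happens after first dose, namely having a scan, while the OS and PFS clocks start at first dose. A participant who dies or withdraws before any scan is therefore removed because of what happened on study.

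Two consequences follow. First, the analysis set for OS and PFS is unclear: the handling rules cover participants whom the population definition has already excluded. Second, a never-scanned participant cannot count as disease-controlled or as a responder, so removing that person shrinks the denominators of DCR and ORR but never the numerators. The plan describes no all-treated DCR or ORR, so a reader would not see the rate among everyone who received the treatment.

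**Working it through.** **1. The two sections side by side.** Take a treated participant with no on-study scan.

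| Outcome | Section 10.2 | Section 10.3.1 |
|---|---|---|
| Dies | Not in the efficacy set | OS event; PFS event on date of death (the primary PFS definition may censor first if new systemic therapy was started) |
| Alive and followed for survival | Not in the efficacy set | OS censored at last known alive date; PFS censored at first dose |
| No follow-up at all | Not in the efficacy set | OS and PFS censored at first dose |

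Nobody in the Response Evaluable population can meet the PFS first-dose condition, because membership requires an on-study assessment. Almost nobody can meet the OS condition, because an on-study scan is itself follow-up. The first row is where the two datasets differ in events.

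**2. Direction for OS.** Inputs, all assumed: S is true survival at time t among all treated participants, d is the share who are unscanned and dead by t, and u is the share who are unscanned, alive and still followed at t. No one is censored before t.

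- Scanned-only estimate = (S − u)/(1 − d − u).
- S = 50%, d = 3%, u = 0: 0.50/0.97 = 51.5%, above the truth.
- S = 50%, d = 3%, u = 5%: 0.45/0.92 = 48.9%, below the truth.
- The estimate exceeds S only when u < d × S/(1 − S). Here that is 0.03 × 0.50/0.50 = 3%.

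The term u matters because participants who stop treatment are still followed for survival every 3 months for about 36 months (Section 5.1, Table 2-4).

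**3. Direction for PFS.** Unscanned participants who do not die are censored at first dose and do not move the Kaplan-Meier curve. Unscanned deaths do. An early one left out raises the curve. A late one counts as a long PFS time, because Section 10.3.1 states no limit for missed scans before death, so leaving it out can lower the curve. The sign depends on when these deaths occur.

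**4. DCR and ORR.** With x successes, n scanned and m never-scanned treated participants, x/(n + m) ≤ x/n for any m ≥ 0. Example for DCR, with x = 22, n = 80 and exact (Clopper-Pearson) 95% CIs:

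| m (assumed) | Rate | 95% CI |
|---|---|---|
| 0 | 22/80 = 27.5% | 18.1 to 38.6 |
| 4 | 22/84 = 26.2% | 17.2 to 36.9 |
| 8 | 22/88 = 25.0% | 16.4 to 35.4 |
| 16 | 22/96 = 22.9% | 15.0 to 32.6 |

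The last row uses the whole planned margin, 96 − 80 = 16. It is an extreme, because Enrolled in Section 10.2 means consented and registered, so some of the 16 may never be dosed.

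**5. The planned test.** Inputs from Sections 10.1 and 10.3.5: 27 then 53 more response-evaluable patients, continue at 7 or more of 27, null 20%, alternative 35%, one-sided 5%, power 85%. The final cutoff is not printed. P(success | p) is the sum over x = 7 to 27 of P(X1 = x) × P(X2 ≥ c − x), with X1 ~ Bin(27, p) and X2 ~ Bin(53, p), treating both stages as using one endpoint.

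- c = 21: alpha 7.45%, above 5%.
- c = 22: alpha 4.94%, power 85.3% at 35%.

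The stated design reproduces with a derived cutoff of 22/80. It is defined on response-evaluable patients, so never-scanned participants do not enter it.

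**The case against.** **The Simon unit is response-evaluable by design.** This stands. Sections 5.2, 10.1 and 10.3.5 all count response-evaluable patients. A reader might infer that leaving out never-scanned participants inflates the type I error of the DCR test. That would require the 20% null to be an all-treated rate, and nothing in the plan reads it that way. For DCR the point is a missing companion estimate, not an error in the test.

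**Leaving out unscanned deaths must flatter OS and PFS.** A reader might infer this too. The documents do not support it: living unscanned participants with follow-up stay in the OS risk set up to their last known alive date, and late unscanned deaths count as long times for both endpoints. The bias can run either way.

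**A censoring rule that nobody meets is redundant, not an opposing instruction.** This is fair for the first-dose rules alone, since censoring at day 0 adds nothing to a Kaplan-Meier curve. But those rules, and the wording of Table 4-1 for PFS, show that a wider set was in mind. The treatment of a death before any scan does differ between the two readings.

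**The SAP will settle it.** It may, and it is not in the supplied text. Section 10.2 nevertheless already states a rule, and a SAP that applied Section 10.3.1 to all treated participants would have to depart from it.

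**The BOR table already has an unable-to-determine category.** That does not rescue the never-scanned. A participant with an unreadable scan can be UTD and still be Response Evaluable.

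**Few will be affected.** Possibly so, given unscheduled scans and continued imaging. The number is not in the documents.

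**Conclusion.** The concern holds in a limited form. The analysis set for OS and PFS is inconsistent: Section 10.2 removes participants, including early deaths, whom Section 10.3.1 is written to handle. This selection on a post-dose event can bias both curves, in a direction and by an amount that cannot be determined from the documents.

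For DCR and ORR the direction is certain and the size is probably modest. With an assumed four never scanned, a DCR of 27.5% becomes 26.2%, a shift of 1.3 points inside a confidence interval about 20 points wide. Even the extreme of 16 gives 22.9%, a shift of 4.6 points. The planned Simon test keeps its alpha of 4.9% and power of 85.3%, given the derived cutoff of 22/80 and one endpoint for both stages.

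This should be settled before database lock, so that the OS and PFS set is not chosen with the data in view.

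**What to change.** - In Section 10.2, name all treated participants (the existing Safety population) as the analysis set for OS and PFS, and apply the event and censoring rules of Section 10.3.1 as written.
- Keep Response Evaluable for the Simon decision at both stages, and state that the 20% and 35% rates refer to that denominator.
- In Section 10.3.1, also report DCR and ORR with exact 95% CIs in all treated participants. Count the never-scanned as UTD in the BOR table, as not disease-controlled and as non-responders, and state how many there are.
- Carry the same wording into the SAP.

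The cost is text only. Section 10.3.2 already analyses safety in all treated participants and survival follow-up is already planned, so no new data are needed. The stage sizes, cutoff, alpha and power do not change. The downside is that the all-treated DCR and ORR may be slightly less favourable than the response-evaluable figures.
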